### 5.3.2 Urinary and Genital Infections

The following is presented to assist in the classification and management of infections of the urinary and genital tracts in studies with dapagliflozin. It is not intended to supplant investigators' clinical judgement.

#### Urinary Tract Infections

If based on the suggestive signs or symptoms (dysuria, urgency or frequency of urination, suprapubic or perineal discomfort, flank, back, or abdominal pain, costovertebral angle tenderness, nausea, vomiting, fever, chills, or sepsis) the investigator believes that a urinary tract infection may be present, urine cultures (in a local laboratory) should be obtained to confirm a presumptive diagnosis of cystitis, urinary tract infection, pyelonephritis, or prostatitis. Mid-stream clean catch urine collections are recommended. Clinical judgement and local standards of care should apply to decisions concerning therapy. Any treatment needs to be documented in the eCRF.

Between scheduled visits, subjects may experience novel signs or symptoms that are potentially indicative of urinary or a genital tract infection. The subject should contact the investigator by telephone. An unscheduled visit will be planned as soon as possible, preferably within 24 h. The investigator will take the subject's recent history, a midstream urine sample will be obtained for urine analyses and a mandated urine culture, and it is also recommended that a genital swab is done, if indicated. Analyses and culture(s) are to be performed at the local laboratory. The

investigator will follow local guidelines to recommend treatment for urinary tract infection or genital tract infection.

Investigational product should be temporary stopped in subjects with clinical evidence of upper urinary tract infection (eg, pyelonephritis) or presumed urosepsis until the course of treatment of the infection has been completed and clinical recovery has occurred. It is recommended that a follow-up urine culture is obtained within 7 days of clinical recovery from a documented UTI. Whether additional therapy is prescribed because of culture results should be determined by Investigator judgement.

### **Genital Tract Infections**

The diagnosis of vaginitis, vulvovaginitis, vulvitis or balanitis can be made based on physical examinations, culture of secretions or a therapeutic response to treatment of fungal or other vaginal pathogens. A urine culture is not required for diagnosis of genital infections if the diagnosis is confirmed by physical examination, culture of secretions, or a therapeutic response to treatment of fungal or other vaginal pathogens. Any treatment needs to be documented in the eCRF.

### **5.3.3 Volume Depletion**

Patients at risk of volume depletion due to co-existing conditions or concomitant medications should have careful monitoring of their volume status as judged by the Investigator. Events of volume depletion include dehydration, hypovolemia, or hypotension.

### **5.3.4 Diabetic ketoacidosis**

Patients treated with study medication who present with signs and symptoms consistent with ketoacidosis, including nausea, vomiting, abdominal pain, malaise and shortness of breath, should be assessed for ketoacidosis, even if blood glucose levels are < 14 mmol/l (250 mg/dl). If ketoacidosis is suspected, discontinuation or temporary interruption of study drug should be considered and the patient should be promptly evaluated.

### **5.3.5 Renal Events**

Renal events are defined by doubling of serum creatinine, dialysis and renal transplantation

### 5.3.6 Hospitalization for Heart Failure

Patients who present with symptoms of heart failure and get hospitalized for more than 24 hours need to be evaluated further to understand the reason for new or worsening of heart failure symptoms.

HF is defined as an event that meets all of the following criteria:

- Admitted to the hospital with a primary diagnosis of HF
- Length-of-stay in hospital extends for at least 24 hours
- Exhibits documented new or worsening symptoms due to HF on presentation, including at least one of the following:
  - Dyspnea (dyspnea with exertion, dyspnea at rest, orthopnea, paroxysmal nocturnal dyspnea); decreased exercise tolerance; fatigue; other symptoms of worsened end-organ perfusion or volume overload
- Physical examination finding considered to be due to HF, including new or worsened:
  - Peripheral edema
  - Increasing abdominal distension or ascites (in absence of primary hepatic disease)
  - Pulmonary rales/crackles/crepitations
  - Increased jugular venous pressure and/or hepatojugular reflux
  - S3 gallop
  - Clinically significant or rapid weight gain thought to be related to fluid retention
- Laboratory evidence of new or worsening HF, if obtained within 24 hours of presentation, including:
  - Increased BNP/N-terminal pro-BNP (NT-proBNP) concentrations consistent with decompensation of HF (such as BNP > 500 pg/mL or NT-proBNP > 2,000 pg/mL),
  - Radiological evidence of pulmonary congestion
  - Non-invasive or invasive diagnostic evidence of clinically significant elevated left- or right-sided ventricular filling pressure or low cardiac output.  
OR
  - Invasive diagnostic evidence with right heart catheterization showing a pulmonary capillary wedge pressure (pulmonary artery occlusion pressure)  $\geq 18$  mm Hg, central venous pressure  $\geq 12$  mm Hg, or a cardiac index  $< 2.2$  L/min/m^2

- Receives initiation or intensification of treatment specifically for HF, including at least 1 of the following:
  - Augmentation in oral diuretic therapy
  - Intravenous diuretic, inotrope, or vasodilator therapy
  - Mechanical or surgical intervention, including:
    - Mechanical circulatory support (e.g., intra-aortic balloon pump, ventricular assist device)
    - Mechanical fluid removal (e.g., ultrafiltration, hemofiltration, dialysis)

## **6 SAFETY REPORTING AND MEDICAL MANAGEMENT**

The Principal Investigator is responsible for ensuring that all staff involved in the study are familiar with the content of this section.

### **6.1 Definition of adverse events**

An adverse event is the development of any untoward medical occurrence in a subject or clinical study subject administered a medicinal product and which does not necessarily have a causal relationship with this treatment. An AE can therefore be any unfavourable and unintended sign (e.g. an abnormal laboratory finding), symptom (for example nausea, chest pain), or disease temporally associated with the use of a medicinal product, whether or not considered related to the medicinal product.

The term AE is used to include both serious and non-serious AEs and can include a deterioration of a pre-existing medical occurrence. An AE may occur at any time, including run-in or washout periods, even if no study treatment has been administered.

### **6.2 Definitions of serious adverse event**

A serious adverse event is an AE occurring during any study phase (i.e., run-in, treatment, washout, follow-up), that fulfils one or more of the following criteria:

- Results in death
- Is immediately life-threatening
- Requires in-subject hospitalisation or prolongation of existing hospitalisation
- Results in persistent or significant disability or incapacity.
- Is a congenital abnormality or birth defect

- Is an important medical event that may jeopardize the subject or may require medical intervention to prevent one of the outcomes listed above.

For further guidance on the definition of a SAE, see Appendix A to the Clinical Study Protocol.

## **6.3 Recording of adverse events**

### **6.3.1 Time period for collection of adverse events**

Adverse Events will be collected throughout the treatment period and including the follow-up period of one week after end of study. SAEs will be recorded from the time of informed consent.

### **6.3.2 Follow-up of unresolved adverse events**

Any AEs that are unresolved at EOS visit are followed up by the Investigator for as long as medically indicated, but without further recording in the CRF. AstraZeneca retains the right to request additional information for any subject with ongoing AE(s)/SAE(s) at the end of the study, if judged necessary.

### **6.3.3 Variables**

The following variables will be collect for each AE;

- AE (verbatim)
- The date when the AE started and stopped
- Select the appropriate as required: maximum intensity or intensity or changes in intensity
- Whether the AE is serious or not
- Investigator causality rating against the Investigational Product (yes or no)
- Action taken with regard to investigational product
- AE caused subject's withdrawal from study (yes or no)
- Outcome.

In addition, the following variables will be collected for SAEs:

- Date AE met criteria for serious AE
- Date Investigator became aware of serious AE

- AE is serious due to
- Date of hospitalisation
- Date of discharge
- Probable cause of death
- Date of death
- Autopsy performed
- Causality assessment in relation to Study procedure(s)
- Causality assessment to other medication
- Description of AE.

It is important to distinguish between serious and severe AEs. Severity is a measure of intensity whereas seriousness is defined by the criteria in Section 6.2. An AE of severe intensity need not necessarily be considered serious. For example, nausea that persists for several hours may be considered severe nausea, but not a SAE unless it meets the criteria shown in Section 6.2. On the other hand, a stroke that results in only a limited degree of disability may be considered a mild stroke but would be a SAE when it satisfies the criteria shown in Section 6.2.

#### **6.3.4 Causality collection**

The Investigator will assess causal relationship between Investigational Product and each Adverse Event, and answer 'yes' or 'no' to the question 'Do you consider that there is a reasonable possibility that the event may have been caused by the investigational product?'

For SAEs causal relationship will also be assessed for other medication and study procedures. Note that for SAEs that could be associated with any study procedure the causal relationship is implied as 'yes'.

A guide to the interpretation of the causality question is found in Appendix A to the Clinical Study Protocol.

#### **6.3.5 Adverse events based on signs and symptoms**

All AEs spontaneously reported by the subject or reported in response to the open question from the study site staff: or revealed by observation will be collected and recorded in the CRF. When collecting AEs, the recording of diagnoses is preferred to recording a list of signs and symptoms. However, if a diagnosis is known and there are other signs or symptoms that are not generally part of the diagnosis, the diagnosis and each sign or symptom will be recorded separately.

### 6.3.6 Adverse events based on examinations and tests

The results from the Clinical Study Protocol mandated laboratory tests and vital signs will be summarised in the CSR. Deterioration as compared to baseline in protocol-mandated laboratory values and vital signs should therefore only be reported as AEs if they fulfil any of the SAE criteria or are the reason for discontinuation of treatment with the investigational product.

If deterioration in a laboratory value/vital sign is associated with clinical signs and symptoms, the sign or symptom will be reported as an AE and the associated laboratory result/vital sign will be considered as additional information. Wherever possible the reporting Investigator uses the clinical, rather than the laboratory term (e.g., anaemia versus low haemoglobin value). In the absence of clinical signs or symptoms, clinically relevant deteriorations in non-mandated parameters should be reported as AE(s).

Any new or aggravated clinically relevant abnormal medical finding at a physical examination as compared with the baseline assessment will be reported as an AE

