### 5.2.1 Laboratory safety assessments

Blood samples shall be collected and processed as per the local affiliated laboratory criteria.

Deterioration as compared to baseline in protocol-mandated laboratory values, vital signs and other safety variables will only be reported as AEs if they are clinically significant, fulfil any of the SAE criteria or are the reason for discontinuation of treatment with the investigational product, or require the subject to receive specific corrective therapy. If a deterioration in a laboratory value/vital sign is associated with clinical signs and symptoms, the sign/symptom will be reported as an AE and the associated laboratory result/vital sign will be considered as additional information. Any new or aggravated clinically relevant abnormal medical finding at a physical examination or ECG evaluation as compared with the baseline assessment will be reported as an AE.

Clinically relevant deterioration in non-protocol-mandated measurements will be reported as AE(s).

Wherever possible the reporting investigator uses the clinical, rather than the laboratory term (eg, anaemia versus low haemoglobin value).

The following laboratory variables will be measured:

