**Table 2 Laboratory Safety Variables**

Haematology/Haemostasis (whole blood)	Clinical Chemistry (serum or plasma)
B- Hematocrit	S/P-Creatinine
B-Leukocyte count	S/P-Bilirubin, total
B-Leukocyte differential count (absolute count)	S/P-Alkaline phosphatase (ALP)
B-Platelet count	S/P-Aspartate transaminase (AST)
B - Haemoglobin (Hb)	S/P-Alanine transaminase (ALT)
Urinalysis (dipstick)	S/P-Albumin
U-Hb/Erythrocytes/Blood	S/P-Potassium
U-Protein/Albumin	S/P-Calcium, total
U-Glucose	S/P-Sodium
	S/P-Creatine kinase (CK)

*The Investigator should make an assessment of the available results with regard to clinically relevant abnormalities. The laboratory results should be signed and dated and retained at centre as source data for laboratory variables. For information on how AEs based on laboratory tests should be recorded and reported, see Section 6.3*

**NB.** In case a subject shows an AST **or** ALT  $\geq 3 \times \text{ULN}$  **or** total bilirubin  $\geq 2 \times \text{ULN}$  please refer to Appendix B ‘Actions required in cases of combined increase of Aminotransferase and Total Bilirubin – Hy’s Law’, for further instructions.

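### Sections 5.2.1 and 6.3.6 give incompatible rules for when a laboratory or vital-sign deterioration is an AE, so part of the primary AE count depends on which section a site follows

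*Protocol*

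**What the plan says.** Section 5.2.1 of the protocol covers protocol-mandated laboratory values, vital signs and other safety variables. Deteriorations from baseline "will only be reported as AEs if they are clinically significant, fulfil any of the SAE criteria or are the reason for discontinuation" of investigational product, "or require the subject to receive specific corrective therapy". That makes four triggers.

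Section 6.3.6 takes up the same question. Its subject is "Deterioration as compared to baseline in protocol-mandated laboratory values and vital signs", and these "should therefore only be reported as AEs if they fulfil any of the SAE criteria or are the reason for discontinuation of treatment". That makes two triggers. The reason given is that these results will be summarised in the study report anyway.

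The note under Table 2, still within section 5.2.1, tells the reader: "For information on how AEs based on laboratory tests should be recorded and reported, see Section 6.3". It does not say which section prevails if they differ.

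The sections also differ in wording on examinations. Section 5.2.1 says that a new or aggravated relevant "abnormal medical finding at a physical examination or ECG evaluation as compared with the baseline assessment will be reported as an AE". Section 6.3.6 says the same of an "abnormal medical finding at a physical examination as compared with the baseline assessment will be reported as an AE", without naming ECG.

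**The concern.** Section 2.1 makes the AE profile at 24 weeks the primary objective. The Synopsis (Statistical methods) and section 8 report it as number, percentage and annualised rate. The reporting rule decides what enters these figures. If two sections set different rules, two sites can both follow the protocol and still count differently. With one arm and no control group, nothing offsets a difference in ascertainment.

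This is not a matter that the analysis can settle later. Laboratory and vital-sign values can be tabulated afterwards. An investigator's judgement of clinical significance, a causality rating or an AE entry that was never made cannot be recovered in full.

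**Working it through.** The protocol states no figure for this point, so there is none to reproduce. The check is a comparison of the two rules, followed by an illustration of size.

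**Step 1. The two rules case by case** (protocol-mandated laboratory value or vital sign, worse than baseline):

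| Case | 5.2.1 | 6.3.6 |
|---|---|---|
| Meets an SAE criterion | AE | AE |
| Is the reason for stopping the product | AE | AE |
| Comes with signs or symptoms | The sign or symptom is the AE | The sign or symptom is the AE |
| Asymptomatic, non-serious, product continued, clinically significant | AE | Not an AE |
| Asymptomatic, non-serious, product continued, corrective therapy given | AE | Not an AE |
| None of these | Not an AE | Not an AE |

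Both rules are phrased as exclusive, so neither can be read as supplementing the other. The conflict is confined to the fourth and fifth rows.

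**Step 2. Fit with the special-interest events.** Section 2.1 lists renal events and volume depletion among the AEs of special interest. Section 5.3.5 counts a doubling of creatinine as a renal event, and Table 2 makes creatinine a mandated test. Section 5.3.3 counts hypotension as volume depletion, and blood pressure is a mandated measurement (Table 1, section 5.2.4.1). Read literally, section 6.3.6 makes either finding unreportable as an AE when it is asymptomatic, non-serious and does not stop the product. The renal discontinuation criterion in section 3.6 rests on a repeat eGFR below 45, which is a different threshold and need not catch every creatinine doubling.

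**Step 3. Size.** Inputs: N = 200 (section 8), about 8 sites (Synopsis), and q = share of patients with at least one change in the fourth or fifth row. The protocol does not give q. Assumed range: 1% to 15%.

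- Patients affected = 200 × q. q = 1%: 2. q = 5%: 10. q = 10%: 20. q = 15%: 30.
- Maximum shift in patient-level incidence = q, that is 1 to 15 percentage points. The maximum is reached only if none of these patients has any other AE.
- Event counts and the annualised rate change with every such event, whether or not the patient has another AE.

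**Step 4. Comparison with sampling error**, at an assumed incidence of 20% (40 of 200):

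- Exact (Clopper-Pearson) 95% interval: 14.7% to 26.2%, so the arms are 20 − 14.7 = 5.3 and 26.2 − 20 = 6.2 points.
- Normal approximation: 1.96 × √(0.2 × 0.8 / 200) = 5.5 points.
- At q = 5% the largest possible shift is 5 points, which is below both exact arms. The shift reaches the arms at q = 5.3% to 6.2%, that is 200 × 0.053 = 10.6 to 200 × 0.062 = 12.4 patients, or about 11 to 12.

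**The case against.** The strongest reply is that the conflict is narrow. The sections agree on serious events, on changes that stop treatment, on symptomatic changes and on non-mandated tests. Laboratory values and vital signs are primary outcome measures in their own right and are summarised under either rule. Section 6.3.6 also gives a reason for its narrow rule, namely that the data are reported elsewhere. Site training (section 9.1), eCRF instructions (section 5) and monitoring (section 9.2) could each impose a single rule. All of this limits the size of the problem. None of it removes the contradiction or says which text governs.

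Four stronger readings are tempting, and the documents do not support them:

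- **That the sections contradict each other on ECG.** The restriction in 6.3.6 covers laboratory values and vital signs. It is silent on ECG, so "physical examination or ECG evaluation as compared with the baseline assessment will be reported as an AE" in 5.2.1 stands unopposed. This is a gap in wording.
- **That the narrow rule loses the renal, electrolyte and volume signals.** The values are still summarised, and symptomatic, serious or treatment-stopping events are AEs either way. Sections 5.3.3 and 5.3.5 also name hypotension and creatinine doubling as events, though they do not expressly override 6.3.6. What is at risk is classification as an AE.
- **That the definitional gap always matches or exceeds sampling error.** This rests on an assumed q and fails at 5% and below.
- **That between-site differences will be artefact.** Sites can differ for other reasons, and if all sites follow the same section there is no mixing. Mixed application is a risk that the text permits, not a certainty.

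**Conclusion.** The concern holds in a limited form. Two current sections set incompatible exclusive rules for the same data, and nothing in the protocol ranks them. The consequence is confined to asymptomatic, non-serious changes in mandated laboratory values and vital signs that are clinically significant or treated and do not stop the product. For these, the AE number, percentage and annualised rate depend on the section followed. SAE counts and AEs leading to discontinuation do not.

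The size is unknown. Under the assumed 1% to 15%, 2 to 30 of 200 patients have such an event and patient-level incidence shifts by at most 1 to 15 points. That is comparable to sampling error at an assumed 20% incidence only from about 5.3% to 6.2% upward. The contradiction itself does not depend on these assumptions. It should be resolved before data collection, because unrecorded AE entries cannot be fully reconstructed afterwards.

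**What to change.** State one reporting rule, in the same words, in sections 5.2.1 and 6.3.6, and carry it into the eCRF instructions and site training.

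The four-trigger rule of 5.2.1 is the more consistent choice. The two-trigger rule would leave an asymptomatic creatinine doubling or hypotension outside AE reporting, although the primary outcome lists renal events and volume depletion as special-interest AEs. If the sponsor prefers the narrow rule because the values are summarised anyway, 5.2.1 must be cut to match, and the protocol must say how these special-interest events are captured.

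Name ECG findings in the last paragraph of 6.3.6, as an alignment of wording only.

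The cost is one paragraph of protocol text plus training wording. The downside of the four-trigger rule is a somewhat higher AE count than 6.3.6 would give.

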## 2 STUDY OBJECTIVES

### 2.1 Primary objective

Primary Objective:	Outcome Measure:
To describe the adverse events profile of dapagliflozin + saxagliptin fixed dose combinations in Indian T2DM patients at 24 weeks.	
 
• Adverse Events (AEs) including Serious adverse events (SAEs), AEs leading to discontinuation (DAE) and adverse events of special interest (volume depletion, renal events, major hypoglycaemic events, fractures, urinary/genital tract infections diabetic ketoacidosis, amputations and hospitalization for heart failure)
 
• Safety laboratory values
 
• Electrocardiogram (ECG)
 
• Vital Signs (pulse and BP)
 
• Physical examination
 

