### **5.2.4 Vital signs**

Vital signs will be measured and recorded during each on site visit through the study duration.

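### The AE recording rule in section 6.3.6 can leave out a non-serious, asymptomatic creatinine doubling that meets the protocol's own renal-event definition, and section 5.2.1 contradicts that rule

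*Protocol*

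**What the plan says.** Section 2.1 places both event types within the AE part of the primary outcome, which includes "adverse events of special interest (volume depletion, renal events, major hypoglycaemic events, fractures" and further items. The same list names safety laboratory values and vital signs as outcome measures in their own right.

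The definitions are in section 5.3:
- Section 5.3.5: "Renal events are defined by doubling of serum creatinine, dialysis and renal transplantation".
- Section 5.3.3: "Events of volume depletion include dehydration, hypovolemia, or hypotension". No blood-pressure cut-off is given.

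The measurements concerned are mandated. Table 2 lists "S/P-Creatinine", and section 5.2.4 states: "Vital signs will be measured and recorded during each on site visit through the study duration".

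Two sections then say when a worsened mandated value becomes an AE:
- Section 6.3.6 allows two triggers only: the value meets a seriousness criterion, or it is the reason for stopping the investigational product.
- Section 5.2.1 has the same two triggers and adds two more: the value is clinically significant, or the subject needs specific corrective therapy.

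Both sections handle symptomatic cases in almost the same words. In 6.3.6, "the sign or symptom will be reported as an AE and the associated laboratory result/vital sign will be considered as additional information"; in 5.2.1, "the sign/symptom will be reported as an AE and the associated laboratory result/vital sign will be considered as additional information". Both then ask for the clinical term in place of the laboratory term where possible. Section 6.3.5 prefers a diagnosis to a list of symptoms.

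**The concern.** A component of the primary outcome is defined partly by a laboratory value, while the general recording rule of section 6.3.6 is written to keep most such values off the AE page. Neither 6.3.6 nor 5.2.1 exempts findings that meet a section 5.3 definition. For hypoglycaemia the protocol deals with this openly: section 5.3.1 keeps non-serious episodes off the AE page but gives them dedicated eCRF pages. No such route is described for renal or volume-depletion events.

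At stake are the renal and volume-depletion counts in a single-arm safety study of 200 patients. Any error from following 6.3.6 runs downward. Because 5.2.1 sets a wider rule, two sites could also handle the same finding differently, and both could say that they followed the protocol.

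**Working it through.** **Step 1. Set the rules side by side.** Take findings that are not serious and do not stop treatment.

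| Finding | Section 6.3.6 | Section 5.2.1 |
|---|---|---|
| Creatinine doubled, no symptoms, no therapy | Not an AE | AE only if judged clinically significant |
| Creatinine doubled, no symptoms, corrective therapy given | Not an AE | AE |
| Low blood pressure, no symptoms | Not an AE | AE if judged clinically significant or treated |
| Low blood pressure with a symptom such as dizziness | Symptom is the AE; clinical term preferred where possible | Same |
| Dehydration or hypovolaemia diagnosed clinically | Not a reading, so the restriction does not apply | Same |

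Dialysis and transplantation are not readings either, so they are also outside the restriction. The first row is the clear gap: the finding satisfies section 5.3.5, yet 6.3.6 does not make it an AE. The third row is weaker, because without a cut-off in 5.3.3 it is a matter of judgement whether the reading is a volume-depletion event at all. In the fourth row the protocol permits entry as hypotension but does not require it.

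**Step 2. Does the renal stopping criterion close the gap?** Criterion 8 in section 3.6 concerns repeat eGFR values below 45 mL/min/1.73 m2. A doubling that leads to discontinuation on this ground is an AE even under 6.3.6. The protocol names the CKD-EPI formula but does not print it, so I assume that eGFR varies as creatinine to the power -k, with k from 0.8 to 1.2.

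eGFR after doubling = baseline eGFR × 2^(-k). It stays at or above 45 when baseline eGFR ≥ 45 × 2^k.

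| k | 45 × 2^k |
|---|---|
| 0.8 | 78.3 |
| 1.0 | 90.0 |
| 1.2 | 103.4 |

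For example, from a baseline of 110 a doubling gives 110 / 1.741 = 63.2 (k = 0.8), 110 / 2 = 55.0 (k = 1.0) or 110 / 2.297 = 47.9 (k = 1.2), and the criterion is not met under any of the three. A doubling that has recovered by the repeat test does not meet it either. From lower baselines a confirmed doubling would fall below 45 and so become reportable if treatment stops. The criterion therefore covers part of the gap. The share cannot be computed, because the protocol gives no expected distribution of baseline eGFR.

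**Step 3. Timing.** Table 1 schedules post-baseline safety laboratory tests at weeks 8, 16, 24 and 26. Week 24 is the end-of-treatment visit. For a subject who completes treatment, a doubling first found at week 24 or 26 cannot be a reason for stopping, so under 6.3.6 only seriousness would make it an AE.

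**Step 4. What one unrecorded subject means.** With 200 subjects each one is 1/200 = 0.5 percentage points. One recorded event gives 0.5% (exact 95% interval 0.01% to 2.75%); none gives 0% (upper limit 1.83%). This shows how sensitive the count is. It does not estimate how many events would be missed.

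**The case against.** The strongest reply is that 6.3.6 does not stand alone. Under 5.2.1 a clinically significant or treated deterioration is an AE, and a doubled creatinine would ordinarily be judged significant. This stands to the extent that a site following 5.2.1 would record most such cases. It does not remove the point: the two sections contradict each other, and nothing says which governs.

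Second, the preference for clinical terms and diagnoses means that hypotension or dehydration can be entered as such. This too stands, and it makes the symptom sentence a lesser part of the point. The preference is not a requirement, however, and an asymptomatic doubling may carry no diagnosis.

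Third, the investigator may stop treatment for a laboratory abnormality under criterion 5 of section 3.6, or may judge the finding an important medical event and hence serious. Both routes exist, but they depend on case-by-case judgement, whereas 5.3.5 gives a fixed definition.

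Fourth, the SAP, which is not shown, could derive creatinine doubling from the laboratory data. It could, and its absence from section 8 is no fault. It could not reliably recover hypotension entered under a symptom, since 5.3.3 has no cut-off and Visits 3, 4, 6 and 8 are by telephone.

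A reader might infer more than the protocol supports:
- That the events disappear from the study. They do not: creatinine and blood pressure are collected and summarised, and those summaries are themselves primary outcome measures.
- That AE counts are the study's only result. Section 2.1 also lists laboratory values, ECG, vital signs and physical examination, and section 2.2 adds efficacy.
- That both event types are defined wholly by readings. Dialysis, transplantation, dehydration and hypovolaemia are not.

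**Conclusion.** The point holds in a limited form. As written, section 6.3.6 leaves out of the AE record an asymptomatic, non-serious creatinine doubling that does not stop treatment, although section 5.3.5 makes it a renal event within the primary outcome. Section 5.2.1 states a wider rule, so ascertainment depends on which section a site follows. To a lesser degree, the symptom sentence in both sections lets hypotension be entered under its symptom.

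The consequence is a possible under-count in the AE tables, downward in direction and unknown in size. A percentage for it would rest entirely on assumed event rates and assumed missed shares, so none is given. The only calculation that bears on the conclusion is the eGFR threshold of about 78 to 103 mL/min/1.73 m2, which rests on the assumed exponent of 0.8 to 1.2. The correction should be made, because it concerns a primary outcome component and is cheap.

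**What to change.** 1. Reconcile the AE triggers of sections 5.2.1 and 6.3.6 so that one rule applies at all sites.
2. Add the same sentence to both sections, for example: *Any finding that meets a section 5.3 definition of a renal or volume-depletion event is recorded as an AE under that special-interest term, whether or not it is symptomatic, serious or leads to stopping treatment; any accompanying symptom is recorded as well.*

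Deriving creatinine doubling against baseline from the laboratory data is a useful cross-check on the AE record and can be left to the SAP.

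The cost is one aligned rule and one sentence in each of two sections, through the usual protocol-amendment route. No new measurement is needed, and the stopping criteria and patient management are untouched. The downside is slightly higher renal and volume-depletion counts.
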